2.6.2 Sample collection for correlative studies

Peripheral blood as well as tumor and vaccine site biopsy sample collection includes procurement of:

- (i) Peripheral blood mononuclear cells (PBMCs): Leukapheresis samples will be obtained from study subjects prior to initiation of Nivolumab (L1), prior to initiation of vaccination (L2) and after the 3rd vaccine at week 20 (L3). PBMCs will also be obtained by venipuncture on weeks 4, 13, 15, 18, 24 and every 4 weeks thereafter until disease progression.
- (ii) Tumor samples will be obtained from study subjects with unresectable melanoma prior to initiation of Nivolumab (B1), prior to initiation of vaccination (B2), after the 3rd vaccine at week 20 (B3), and at the time of progression (B4). B2 and B3 biopsies will be performed provided that biopsiable disease is present.
- (iii) Vaccine site biopsies will be obtained within 24 hours prior to the 3rd vaccine. One of the 2 vaccines sites will be biopsied as per investigator discretion.

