5. TREATMENT PLAN

Overall Treatment administration

Treatment will be administered on an outpatient basis. Expected toxicities and potential risks as well as dose modifications for Nivolumab and NeoVax plus Montanide and locally administered Ipilimumab, respectively, are described in Section 6 (Expected Toxicities and Dosing Delays/Dose Modification). No investigational or commercial agents or therapies other than those described below may be administered with the intent to treat the patient's malignancy.

Participants will be identified and enrolled on the study if they meet all eligibility criteria. After confirmation of adequate tumor content in the surgical resection/core biopsy specimen (at least 30% tumor in specimen), each participant will start receiving Nivolumab as described in section Section 5.2.1, while vaccine is being prepared. If there is no adequate tumor content in the specimen, the patient will be removed from protocol and replaced. Treatment with NeoVax plus Montanide plus local Ipilimumab will begin within 12 weeks after initiation of Nivolumab. Days will not be counted continuously on protocol therapy. If a toxicity results in a hold of study vaccine administration, counting of days will hold until treatment resumes (e.g. should a patient not be able to receive his/her second vaccine at Week 15 due to a toxicity, counting is held; if the toxicity has resolved a week later, the administration of that second vaccine becomes the participant's new Week 15). Following a dose delay, those day's assessments should be repeated in order to restart participant's vaccinations.

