5.2.1.2 Nivolumab plus neoantigen vaccine (NeoVax plus Montanide) / Ipilimumab Period

Patients will begin therapy with neoantigen vaccine (NeoVax plus Montanide) / Ipilimumab once the vaccine has been prepared and testing completed at week 12. Patients will receive Nivolumab at a flat dose of 480 mg as a 30 minutes (+/- 10 min.) i.v. infusion every 4 weeks (28 days). Nivolumab will be given 60 minutes (+/- 10 min) following local Ipilimumab administration.

If therapy with neoantigen vaccine (NeoVax plus Montanide) / Ipilimumab gets delayed, vaccination timepoints will be modified as follows:

Neoantigen vaccine (NeoVax plus Montanide) / Ipilimumab vaccination timepoints #2 (week 15), #3 (week 18), and #4 (week 21) will be moved accordingly so there is a window of three weeks (+/- 3 days) between each vaccination timepoint. If any of the vaccine administrations coincide with Nivolumab treatment, neoantigen vaccine (NeoVax plus Montanide) / local Ipilimumab will be administrated first and Nivolumab will be given 60 minutes (+/- 10 min) following local Ipilimumab administration.

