9.1.1 Screening *ex vivo* IFN- γ ELISPOT

For each participant, a set of screening peptides will be synthesized. The screening peptides will be 15-17 amino acids in length, overlapping by 11 amino acids and covering the entire length of each peptide or the entire length of the neoORF for neoORF-derived peptides. The set of participant-specific screening peptides will be pooled together (either as a single pool or in four sub-pools corresponding to the immunizing peptide pools) at approximately equal concentration and a portion of each peptide will also be stored individually. In addition, the predicted 9mer or 10mer epitope for each immunizing peptide will be synthesized and pooled. Purity of the peptide pools will be ascertained by testing PBMC from 5 healthy donors with established low background in *ex vivo* IFN- γ ELISPOTs. Initially, PBMC obtained prior to Nivolumab, prior to Vaccination, and at week 20 (the primary immunological endpoint) will be stimulated for 18 hours with the overlapping 15-17mer peptides (11 amino acids overlap) and with the 9mer/10mer epitopes to examine the global response to the peptide vaccine. Subsequent assays may utilize PBMC collected at other time points as indicated. If no response is identified at the primary immunological endpoint using the *ex vivo* IFN- γ ELISPOT assay, PBMC may be stimulated *in vitro* with the peptide pool for a longer time period (up to 10 days) and re-analyzed.

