10. STUDY CALENDAR

Procedure ¹	Screen ²	Pre-Treatment ³	Pre-Vaccination Treatment				Vaccination Treatment								Post Vaccination		Follow Up ¹⁴
			0	4	8	10	12	13	15	16	18	19	20	21	22	24	Q4 weeks
Week	NA																
Informed Consent	X																
Med Hx	X																
Concomitant Medication	X	X	X	X	X	X	X	X	X	X	X	X	X	X	X	X	X
PE/Vitals/Pulse Ox	X		X	X	X	X	X	X	X	X	X	X	X	X	X	X	X
ECOG PS	X		X	X	X	X	X	X	X	X	X	X	X	X	X	X	X
Staging scans ³	X						X									X	X
CBC w/ diff	X		X	X	X	X	X	X	X	X	X	X	X	X	X	X	X
Serum Chem ⁴	X		X	X	X	X	X	X	X	X	X	X	X	X	X	X	X
12-lead EKG	X																
Pregnancy Testing ⁵	X		X	X		X	X		X		X						
Thyroid Stimulating Hormone ⁶	X																
Infectious Panel ⁷	X																
Urinalysis	X																
Blood draw for vaccine manufacturing ⁸	X																
HLA class I and II typing ⁹		X															
Nivolumab administration ¹⁰			X	X	X		X			X			X		X	X	X
Ipilimumab administration ¹¹																	
Neoantigen vaccine Administration ¹²																	
Tumor biopsy ^{11,*}		X ¹¹													X ¹¹		
Leukapheresis ^{12,*}		X ¹²													X ¹²		
Blood draw for immune response monitoring ^{13,*}			X ¹³		X ¹³										X	X	
Vaccine biopsy [*]																	
Adverse Events			X	X	X	X	X	X	X	X	X	X	X	X	X	X	X

*please see Vaccine + Ipilimumab administration and vaccine-related assessments table below

- 1 All study procedures should be performed within +/- 3 day window unless specified otherwise
- 2 Screening assessments must be completed within 30 days of, and prior to the first dose of Nivolumab on Week 0 Day 1. An additional 15 days is allowed for a repeat biopsy, if needed, to obtain adequate tissue for sequencing. This initial biopsy sample should have approximately 30% tumor cellularity and a minimum of 5-8 cores or 100 mm³ in order for sequencing to be completed

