- 11 Tumor biopsies will be collected in patients with unresectable melanoma who have metastatic sites accessible to serial tumor biopsies within two weeks prior to Nivolumab treatment initiation. Tumor biopsy must contain $\geq 30\%$ of tumor cells. At a minimum, 5 core biopsies or a surgical tumor specimen of 100mm³ will be obtained. Skin punch biopsies of a skin lesion are also allowed. The collection of tumor biopsies for research purposes do not apply for patients with stage III melanoma
- 12 Leukapheresis procedure will be performed within 14 days before starting Nivolumab. At each Leukapheresis collection timepoint 2x10 mL EDTA tubes will be collected. These tubes should be dropped off at the IAL upon collection. If Leukapheresis cannot be performed a total of 200mL of blood should be drawn. If starting of vaccine administration gets delayed, week 20 leukapheresis will be collected before vaccination timepoint #4. A Leukapheresis during the Post-Vaccination treatment/ Followup period may be performed
- 13 Unless otherwise specified, 80 mL of blood will be drawn for immune monitoring.
- 14 Active Follow-Up: Participants removed from active study treatment will be followed at the following schedule until initiation of a new therapy for recurrent disease, withdrawal of consent, or death (whichever comes first):
 - At least every 3 months (+/- 2 weeks) for the first 2 years after initiation of study therapy,
 - At least every 4 months (+/- 2 weeks) for the third year after study therapy initiation,
 - At least every 6 months (+/- 4 weeks) thereafter, until 5 years have passed since study therapy initiationLong-Term Follow-Up: Participants removed from active follow-up for progression/initiation of a new therapy will enter long-term follow-up, where they will be followed via medical record review until death for survival. Updates to the CRFs are to be made approximately every six months
- * Please see table below

Neoantigen vaccine + Ipilimumab administration calendar and assessments related to vaccination timepoints

Procedure ¹	Pre-vaccine assessments	Neoantigen Vaccine Dose #1 ^c	Post vaccine dose 1 visit	Neoantigen Vaccine Dose #2 ^c	Post vaccine dose 2 visit	Neoantigen Vaccine Dose #3 ^c	Post vaccine dose 3 visit	Neoantigen Vaccine Dose #4 ^c	Post vaccine dose 4 visit
PE/vitals Concomitant Medications ECOG, CBC w/ diff, Serum Chemistry ²		X	X	X	X	X	X	X	X
Leukapheresis	X ^a							X ^a	
Tumor biopsy	X ^b							X ^b	

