Timelines: We expect to enroll one patient per month. We expect FPFV to occur by September 2020. LPFV is expected for July 2022 and overall duration of the study will be 4 years.

Analysis of Secondary Endpoints

Secondary endpoint in this clinical trial will: (a) assess the induction of IFN- γ T-cell response or tetramer staining to the assay peptides, and (b) to estimate rates of disease progression or recurrence (RECIST 1.1) depending on whether the patient is resected or has measurable disease. Analyses of the secondary endpoint will be based on 15 patients treated at the MTD.

The induction of IFN- γ T-cell response will be based on ELISPOT assessments taken prior to vaccine administration and at week 16. The proportion of patients who achieve more than 55 SFU/10⁶ PBMC or 3 times their baseline level will be presented with a 90% exact binomial

confidence interval. Based on a cohort of size 15, the confidence interval will be no wider than 0.46.

The proportions of patients with disease progression or recurrence, according to melanoma stage, will be presented with 90% exact binomial confidence intervals.

Analysis of Correlative Endpoints

Longitudinal analyses of PBMC immune response kinetics to the peptide pool and to individual epitopes will be presented graphically and descriptively at each time point. Changes in the magnitude of the response relative to pre-treatment at several different time points after vaccination will be summarized descriptively. Changes in response between pre-treatment and 16 weeks post-vaccination, which is the time of the primary immunologic endpoint, will be assessed using the Wilcoxon signed-rank test.

Immune studies of T cell subpopulations (CD4⁺, CD8⁺, central/effector memory cells, Th1/Th2 cells, T-reg, etc.), myeloid-derived suppressor cells (MDSC), CTL response, and T cell activation status will be summarized using descriptive statistics.

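### The neoantigen-response rate is set at week 16, where no immune draw is listed for a patient vaccinated on schedule, and its either/or rule can count a response without a rise

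*Protocol*

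**What the plan says.** - **Time.** Protocol 13.1, on secondary endpoints: "T-cell response will be based on ELISPOT assessments taken prior to vaccine administration and at week 16". The correlative paragraph of 13.1 describes its Wilcoxon signed-rank comparison as "Changes in response between pre-treatment and 16 weeks post-vaccination, which is the time of the primary immunologic endpoint". Protocol 9.1.1 says that PBMC taken before nivolumab, before vaccination and "at week 20 (the primary immunological endpoint) will be stimulated for 18 hours".
- **Samples.** Protocol 2.6.2 schedules leukapheresis before nivolumab (L1), before vaccination (L2) and at week 20 after the third vaccine (L3). It adds: "PBMCs will also be obtained by venipuncture on weeks 4, 13, 15, 18, 24 and every 4 weeks thereafter until disease progression". The vaccination calendar in Section 10 lists draws one week after dose 1, before doses 2 and 3, within three weeks after dose 4, and before nivolumab only once vaccination is over. Its general window is "All study procedures should be performed within +/- 3 day window unless specified otherwise".
- **Rule.** 13.1 counts a patient who exceeds 55 SFU per million PBMC or reaches three times baseline. 9.1.2 sets the first limb at 55 or more.
- **Population.** 13.1 plans 15 patients at the MTD and a 90% exact interval no wider than 0.46. The SAP (Modified Design) reports that the expansion cohort never opened.
- **SAP.** The visible secondary-endpoint list and secondary analyses cover best response and progression or recurrence only.

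**The concern.** Induction of a neoantigen-specific response is the first secondary objective (Protocol 1.3). A responder rate needs one time, one baseline and a rule that separates induction from a response already present. The plan names three times. Its rule can be met without any change. Its Wilcoxon baseline is called pre-treatment, which could mean L1.

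Between L1 and L2 an on-schedule patient receives nivolumab at weeks 0, 4 and 8. Protocol 2.4.3 says that checkpoint inhibitors are thought to work by amplifying T cells already present, and 2.4.4 expects vaccination to expand existing populations. A change from L1 would therefore include the nivolumab run-in, and the rate could include responses that predate the vaccine. With few patients, the choice of time, baseline and denominator can decide the figure reported.

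**Working it through.** **1. The plan's interval.** Inputs from 13.1: n = 15, 90% exact. The Clopper-Pearson limits are the Beta quantiles B(0.05; x, n−x+1) and B(0.95; x+1, n−x). The widest case is x = 7 or 8: 8/15 gives 0.300 to 0.756, width 0.456, which rounds to 0.46. The stated figure is correct for n = 15.

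**2. Endpoint times against listed samples** (doses at weeks 12, 15, 18 and 21).

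| Reading | Study week | Doses before it | Listed immune sample |
|---|---|---|---|
| 13.1, secondary | 16 | 2 | none |
| 9.1.1 | 20 | 3 | L3 leukapheresis |
| 13.1, correlative, from dose 1 | 12 + 16 = 28 | 4 | four-weekly draw |
| 13.1, correlative, from dose 4 | 21 + 16 = 37 | 4 | none (series gives 36) |

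With week w at day 7w ± 3, week 15 is days 102–108, week 16 is days 109–115 and week 18 is days 123–129. The neighbouring windows do not reach week 16. The main calendar table is broken in the text read here, so this rests on the lists in 2.6.2 and in the vaccination calendar notes.

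**3. Delayed vaccine start.** Section 5.2.1.2 says "vaccination timepoints #2 (week 15), #3 (week 18), and #4 (week 21) will be moved accordingly". The week count is stopped only for toxicity (Section 5: "If a toxicity results in a hold of study vaccine administration, counting of days will hold until treatment resumes"). Assume that study weeks run on during a preparation delay of d weeks, so that dose k falls at week 12 + d + 3(k − 1).

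- Doses before week 16: two at d = 0, one at d = 1 to 3, none at d = 4 or more.
- At d = 1 the draw before dose 2 falls at 15 + 1 = 16. At d = 3 the draw one week after dose 1 falls at 12 + 3 + 1 = 16. Each follows one dose only.
- L3 moves with the doses: "If starting of vaccine administration gets delayed, week 20 leukapheresis will be collected before vaccination timepoint #4".

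**4. The responder rule on example values** (SFU per million PBMC; second limb read as at least three times baseline).

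| Before → after | 13.1 either/or | Both limbs required |
|---|---|---|
| 60 → 60 | responder | no |
| 200 → 60 | responder | no |
| 2 → 6 | responder | no |
| 0 → 0 | responder (0 ≥ 3 × 0) | no |
| 100 → 250 | responder | no (250 < 300) |

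A change from 20 to 55 fails in 13.1 (55 is not above 55, and 55 < 60) but passes the 9.1.2 wording.

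**5. Actual n.** The documents give no final numbers. Full cohorts of five (assumed) give 5 patients at the MTD or 10 pooled.

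- Widest 90% exact interval: 3/5 gives 0.189 to 0.924, width 0.73; 5/10 gives 0.222 to 0.778, width 0.56.
- One patient counted without a rise adds 1/5 = 20 points or 1/10 = 10 points.
- Smallest two-sided exact signed-rank p: 2/2⁵ = 0.0625 at n = 5, and 2/2¹⁰ = 0.002 at n = 10. 13.1 does not limit this test to MTD patients.

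**The case against.** **Samples may exist at the intended time.** If week 16 meant 16 weeks after dose 1, that is week 28, where a draw is listed. The text does not say this, and it would still conflict with week 20 in 9.1.1. A reader might also infer that no patient could ever have a week-16 sample. That is too strong. Besides the delays shown above, using both windows late puts dose 1 on day 87 and dose 2 on day 87 + 24 = 111, so the pre-dose-2 draw lands inside week 16. That draw, too, follows one dose.

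**Week labels may follow the doses.** Section 10 still calls the sample before dose 4 the week-20 sample when vaccine start is delayed. If all labels shift this way, the count of two, one or no doses at week 16 does not arise. This stands, and it is why that count is conditional.

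**The size is unknown.** If a share f of patients starts above 55 SFU and stays there without a rise, the rate is too high by f, but that is true by definition. The documents give no f, so they do not support a reading that the rate is inflated by a known amount. 13.1 also plans descriptive kinetics at each time point, where a flat response would show. The rate itself would still count it.

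**Two baselines can both be legitimate.** The objective concerns the vaccine given with nivolumab and ipilimumab, so a change from L1 is defensible if labelled as such.

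**The SAP.** A reader might infer that the sponsor dropped the endpoint. A part of the SAP after the secondary-endpoint list was not available here, and 13.1 still specifies the analysis. What can be said is that the visible analysis section contains no immune analysis.

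**Conclusion.** The concern holds for the definition of the endpoint. On schedule, the week set in 13.1 has no listed immune draw, the documents name other times for the same endpoint, and the first limb of the rule requires no rise. The second limb has no floor. At a baseline of 0 it is trivially met, not undefined, as a reader might suppose. Nor is the plan silent apart from the rule: 13.1 also fixes a pre-vaccine baseline for the rate, the MTD population and a 90% exact interval.

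The bias cannot be sized and may be zero. What can be sized is the loss of precision, 0.73 or 0.56 against 0.46, and the weight of one patient, 20 or 10 points. Both rest on assumed full cohorts of five. The endpoint is estimation only and drives no dose decision, so this should be corrected but does not threaten the primary analysis.

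**What to change.** 1. In Protocol 13.1 and the SAP, base the responder rate on one pair of scheduled samples: L2 (before dose 1) and L3 (the week-20 leukapheresis before dose 4). Section 9.1.1 already plans to assay both first. State that the time was clarified after accrual stopped. State which sample is the Wilcoxon baseline; if it is L1, say that the change includes nivolumab.
2. Keep the prespecified either/or rate, with one threshold wording that reconciles 9.1.2 with 13.1, and name the peptide pool it uses (9.1.1 tests overlapping 15–17mers and 9/10mer epitopes). Beside it, labelled as added after accrual stopped, report one rate that also requires a rise from L2, for example above 55 SFU and at least three times L2. List each patient's L2 and L3 values by pool.
3. Use one stated denominator, vaccinated patients at the MTD, and give the number without a pair. Section 5.4.3 does not settle this, because it refers to a priming phase and a first boost that the four-dose schedule does not label. Replace the 0.46 with the 90% exact interval for the actual n.

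The cost is wording, one added rate and a listing. No new sample type is needed, although the documents do not say how many L2 and L3 samples were collected. The rise-required rate cannot exceed the either/or rate and misses true boosts below threefold, such as 100 to 250, so it stands beside the prespecified rate and does not replace it. L3 precedes dose 4, so later draws remain descriptive.

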True rate of DLT (%)	Probability of Dose Expansion (%)
10	92
20	74
30	53
40	34
50	19
60	9

If the true probability of DLT is 10% or less, then the probability of proceeding to dose expansion is at least 92%. The probability of dose expansion is less than 50% if the true rate of dose-limiting toxicities is 32% or greater.

Minimum vaccination requirement to pass DLT observation period: A minimum of 2 vaccinations and absence of DLTs are required for a patient to complete the 7-week DLT observation period successfully.

Expansion Cohort: When the recommended dose has been determined, an expansion cohort of 10 patients will be treated to assess the performance of the vaccine and to gain additional information about toxicities. Because of the long lead time between patient registration and first vaccination, patients in the expansion cohort may be registered to the trial while safety in the initial cohort(s) is being assessed. Patients in the expansion cohort will not be treated until the safety evaluation of the initial cohorts is complete.

Stopping rule for Expansion Cohort: If four or more patients in the expansion cohort experience dose limiting toxicity (DLT) during the first 7 weeks of treatment, then the dose expansion cohort will be determined to have unacceptable toxicity and the study will be stopped prior to completion of enrollment of the expansion cohort. The table below summarizes the probability of observing 4 or more DLTs within the 10 patients of the expansion cohort for varying underlying rates of toxicity.

	True, but unknown, toxicity rate					
	5%	10%	20%	30%	36%	40%
Probability of observing 4 or more patients with DLT	0.001	0.013	0.121	0.350	0.513	0.618

If the true probability of DLT in the expansion cohort is higher than 35%, then the probability is at least 50% of observing 4 or more patients with DLT within the 10 patients of the expansion cohort.

Total Sample Size: The final sample size for this trial will depend upon the number of dose-escalation cohorts; however, the number of patients treated will be between 4 and 20. The minimum number of patients to be treated is based on observing DLTs after the first dose of Neoantigen Vaccine in the first two patients of Cohort 1 and similarly in Cohort 2. The maximum would occur if two dose-escalation cohorts were treated, with an additional 10 patients at the MTD.

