**DFCI Protocol #: 18-279**

**Statistical Analysis Plan**

**November 20, 2023**

**Design:** The study is an open label, phase Ib trial in which patients with stage III B/C/D or stage IV melanoma were treated with NeoVax plus Montanide® ISA-51 VG in combination with nivolumab and locally administered ipilimumab. Tumor from a surgical resection specimen or core needle biopsy of a melanoma metastasis was used to prepare DNA and RNA for sequencing. Patients began treatment with nivolumab, and vaccine was prepared during the initial 12 weeks of nivolumab therapy. At week 12, patients began vaccination with up to 20 neoantigen peptides. These peptides were encoded by non-silent mutations that were identified through DNA and RNA sequencing. Up to 20 peptides of approximately 20 amino acids in length were prepared for each patient and were administered together with the immune adjuvant poly-ICLC and Montanide® ISA-51 VG, a mineral oil-based immune adjuvant analogous to incomplete Freund's adjuvant (IFA).

Concurrently with the vaccine and nivolumab, ipilimumab was delivered via subcutaneous injection in proximity to each vaccination site to 1) direct anti-CTLA-4 activity to the vaccine-draining lymph nodes, and 2) limit systemic toxic effects. This approach has been shown to be effective in animal tumor models and was expected to result in significantly reduced levels of systemic ipilimumab compared to the approved dose/schedule in advanced melanoma (3 mg/kg q3wks for four doses in the metastatic setting). The ipilimumab dose would be escalated/de-escalated from 2.5 mg/kg flat dose per injection in Cohort 1. Serial tumor biopsies and vaccine site biopsies were performed as shown in the schema below.

The primary endpoint is the rate of DLTs (CTCAE V5.0), as outlined and defined in Section 5.5 of the protocol. We chose dose escalation cohorts of five patients, rather than a more traditional 3+3 design, because the determination of whether to treat at a different dose in this trial was made over a longer period due to the time needed for vaccine preparation and the extended period for safety evaluation. Three dosing cohorts were considered, each varying the dose of ipilimumab. The decision rule to escalate to the next dose was based on having zero or one patient (out of five) experiencing a DLT during the first 42 days of vaccine therapy. The first cohort, Cohort 1, was treated with Ipilimumab 2.5 mg per injection site.

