If zero or 1 patient in Cohort 1 experienced a dose limiting toxicity (DLT) during the first 7 weeks of treatment, 5 patients would be treated as Cohort 2 (Ipilimumab 5 mg per injection site). If two or more patients in Cohort 1 experienced a DLT during the first 7 weeks of treatment, then 5 patients would be treated at Cohort -1 (Ipilimumab 1.25 mg per injection site). If none or 1 patient experienced a DLT on Cohort 2, then Ipilimumab at 5 mg per injection site would be the maximum tolerated dose (MTD) and an additional 10 patients will be treated at that dose level to increase the likelihood of detecting serious

toxicities, to complete biologic correlative endpoints, and to gain preliminary experience with clinical tumor activity. If two or more patients in Cohort 2 experienced DLT, then Dose Level 1 would be the MTD and an additional 10 patients would be treated in an expansion cohort at this dose.

If no or only 1 patient experienced a DLT on Cohort -1, then Ipilimumab 1.25 mg per injection site would be the MTD and an additional 10 patients would be treated in an expansion cohort at that dose level. If two or more patients in Cohort -1 experienced DLT, then the study will be stopped and no MTD would be declared.

The table below shows the probability of moving to the dose expansion phase (0 or 1 patients with DLT out of 5 patients at the MTD) for various possible values of the true, but unknown, toxicity rate.

True rate of DLT (%)	Probability of Dose Expansion (%)
10	92
20	74
30	53
40	34
50	19
60	9

If the true probability of DLT is 10% or less, then the probability of proceeding to dose expansion is at least 92%. The probability of dose expansion is less than 50% if the true rate of dose-limiting toxicities is 32% or greater.

**Minimum vaccination requirement to pass DLT observation period:** A minimum of 2 vaccinations and absence of DLTs are required for a patient to complete the 7-week DLT observation period successfully.

**Modified Design:** Due to slow accrual in this trial, enrollment to the expansion cohort did not begin and trial accrual was stopped at the end of the dose escalation phase, at the time the MTD was determined.

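### Once the expansion was cancelled, the 15 patients at the MTD and the 0.46 interval width no longer describe the secondary analyses, and the SAP does not restate them

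*Protocol*

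**What the plan says.** Protocol section 13.1, under Analysis of Secondary Endpoints, fixes the analysis number: "Analyses of the secondary endpoint will be based on 15 patients treated at the MTD". For the ELISPOT endpoint, the proportion of responders "will be presented with a 90% exact binomial" confidence interval, and the protocol adds: "Based on a cohort of size 15, the confidence interval will be no wider than 0.46". It also promises 90% exact intervals for progression or recurrence by melanoma stage, without giving a width for them.

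The 15 are one escalation cohort of 5 at the chosen dose plus the expansion described in the same section: "When the recommended dose has been determined, an expansion cohort of 10 patients will be treated".

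The SAP of November 20, 2023 keeps the cohort size ("We chose dose escalation cohorts of five patients, rather than a more traditional 3+3 design") and then reports under Modified Design: "Due to slow accrual in this trial, enrollment to the expansion cohort did not begin and trial accrual was stopped". The stop came "at the time the MTD was determined".

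The available SAP text lists two secondary endpoints, best response and progression/recurrence, both summarised as counts. For best response, rates use the cohort as denominator. It contains no confidence interval, no IFN-γ analysis and no restated precision.

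**The concern.** The protocol's only precision statement for the immune-response endpoint depends on an expansion that did not take place. A reader who has the protocol would expect a response rate from 15 patients at one dose, with an interval less than half the unit range wide. The truncated design can give an interval that covers nearly three quarters of that range.

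The analysis set also becomes ambiguous. Read literally, the MTD set is now 5 patients, while a summary over both dose levels could use up to 10. If the SAP does not say which is reported, and with what precision, the choice can be made after the results are seen. The protocol intends to publish even after early termination (section 14), so the figures may well be quoted.

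**Working it through.** **Inputs**
- Planned number: 5 (escalation cohort) + 10 (expansion) = 15 at the MTD (Protocol 13.1).
- Interval: two-sided 90% exact binomial (Protocol 13.1), so 0.05 in each tail.
- Expansion patients enrolled: 0 (SAP, Modified Design).
- Left by design: 5 + 0 = 5 at the MTD, and at most 5 + 5 = 10 over two dose levels.
- No other visible rule adds treated patients to a dose level. The replacement rule in Protocol section 5 concerns inadequate tumor content and applies before treatment starts.

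**Formula (Clopper-Pearson), x responders of n**
- Lower limit L = 0.05 quantile of Beta(x, n − x + 1), with L = 0 if x = 0.
- Upper limit U = 0.95 quantile of Beta(x + 1, n − x), with U = 1 if x = n.
- Width = U − L; the bound is the maximum over x = 0, …, n.

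**The plan's own figure**

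At n = 15 the maximum falls at x = 7 (0.244 to 0.700) and x = 8 (0.300 to 0.756). The width is 0.456, which rounds to the stated 0.46. At n = 14 the maximum is already 0.473, so 15 is the smallest number that meets the bound.

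**Without the expansion** (widths from unrounded limits)

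| n | Maximum width | Where |
|---|---|---|
| 15 | 0.456 | 7/15 or 8/15 |
| 10 | 0.555 | 5/10 (0.222 to 0.778) |
| 5 | 0.734 | 2/5 (0.076 to 0.811) or 3/5 (0.189 to 0.924) |
| 4 | 0.805 | 2/4 |
| 3 | 0.848 | 1/3 or 2/3 |

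**Every outcome at n = 5**
- 0/5 or 5/5: width 0.451. For 0/5 the upper limit is 1 − 0.05^(1/5) = 1 − 0.549 = 0.451.
- 1/5 or 4/5: width 0.647.
- 2/5 or 3/5: width 0.734.

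Only the two extreme outcomes stay within 0.46. The worst case is 0.734 / 0.46 = 1.6 times the stated bound.

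**At n = 10**, results of 0, 1, 9 or 10 responders stay within 0.46 (widths 0.259 and 0.389). From 2/10 to 8/10 the width is 0.470 or more.

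**If fewer are evaluable.** Protocol 5.4.3 ties immunologic evaluability to completed priming plus a boost, so the evaluable number may be below the number treated. With 4 evaluable patients even 0/4 or 4/4 gives a width of 0.527, and no outcome meets 0.46.

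**The case against.** The strongest reply is that nothing was miscalculated. The protocol sentence is conditional on a cohort of 15 and correct for it, and the SAP openly discloses the early stop and its reason. That stands. A reader might infer an arithmetic error in the protocol, but the documents show a correct planning figure whose premise later fell away.

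Second, the SAP has already moved to a per-cohort denominator. That is so for best response, and it deserves credit. It does not extend to the IFN-γ proportion or to the progression/recurrence intervals, which are the analyses tied to 15 patients in the protocol.

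Third, the available SAP text has no IFN-γ analysis and no interval, so there is nothing in it to which a width could attach. This is partly right. It also leaves the protocol's statement as the only one on record, which is a reason for the SAP to replace it.

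Fourth, the bound is not bound to fail. The protocol's background (sections 2.4.4 and 2.6.1) reports responses in all 6 patients tested in the earlier melanoma trial. If 5/5 respond, the interval is 0.549 to 1, inside 0.46. This stands too. One cannot say that the interval will be too wide, or that five patients tell us almost nothing, only that the guarantee is gone.

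Two further inferences are tempting and unsupported:
- *That the signed-rank test cannot reach significance.* The protocol puts this test under Analysis of Correlative Endpoints, with no restriction to MTD patients, no alpha and no sidedness. At most one may note that an exact two-sided test on 5 pairs has a minimum p of 2/2^5 = 0.0625; on 10 pairs it is 2/2^10 = 0.002.
- *That all vaccinated patients should become the main immune set.* The planned vaccine is the same at every level, but local ipilimumab is what is escalated, and Protocol 2.5 expects it to enhance priming, which bears on the immune outcome itself. Some doses may also be given without Montanide (Protocol 5.2). Because the SAP postdates the end of accrual, choosing a new main set now would be post hoc.

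**Conclusion.** The point holds as a failure to update. The stated size and precision belong to a design that was not completed, and the available SAP text does not replace them. By design the number at the MTD falls from 15 to 5, and the maximum 90% exact width rises from 0.456 to 0.734. A pooled summary of 10 would reach 0.555, still above the stated bound.

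This rests on three assumptions:
- The interval is Clopper-Pearson, which reproduces the protocol's 0.46.
- The counts of 5 and 10 are design figures. The documents do not give the numbers actually treated or evaluable. A pooled total may be below 10, because the protocol's sample-size paragraph allows for a cohort ending after DLTs in its first two patients.
- The SAP text available here contains no restatement elsewhere.

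The matter concerns secondary, descriptive summaries. It does not touch the primary endpoint, the DLT rate.

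**What to change.** Amend the SAP as follows.

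1. State that the 15 MTD patients and the 0.46 width no longer apply. Give the actual evaluable number at each dose level and the maximum 90% exact width that follows: about 0.73 for 5, and about 0.56 for any pooled summary of 10. If these are worded as upper bounds, round up to 0.74 and 0.56. If fewer are evaluable, use the matching figure (0.805 for 4).
2. Show the IFN-γ response proportion with exact intervals by dose level. Label any pooled result descriptive.
3. Apply the same restatement to the progression/recurrence intervals. The protocol splits these by melanoma stage, so each group has at most 5 patients per dose level, and often fewer.
4. If the signed-rank test is reported, state the number of pairs. No other change to that test is called for.

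The cost is a short change of wording. No data collection or design change is needed; the price is a less favourable precision statement.
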